3.2. Discussion of Study Design

This study is an open-label investigation because the study endpoints are not believed to be subject to bias.

This study will not be randomized as all subjects within a group will receive the same study treatment, and because of the need to conduct the Chinese groups in sequential order. Because of the sequential nature, Chinese subjects cannot be randomized to dose level as the timing for each group will differ and may affect subject availability.

Subcutaneous injection was chosen because this is the intended clinical route of administration.

Conducting the study in healthy subjects mitigates the potential confounding effects of the disease state and concomitant medications.

3.3. Selection of Doses in the Study

AMG 592 doses were selected based on safety, PK, and PD results from the completed FIH study (20140324), PK study in Japanese healthy subjects (20180132), multiple-dose study in RA patients, ongoing multiple SC dose Phase 1b studies in patients with chronic GvHD and patients with SLE, as well as results from GLP toxicology studies in cynomolgus monkeys. The high dose of CCI [REDACTED] was chosen to evaluate the PK/PD response and because it is within the anticipated upper range of doses that will be used in Phase 2 and 3 studies. Results from Studies 20140324 and 20180132 as well as preliminary Phase 1b data indicate that AMG 592 is well

tolerated at doses up to **CCI** with acceptable safety and Treg selectivity. Exposures in the present study are anticipated to be lower than those at the NOAEL (exposure multiples of at least 16.3 and 3 for AUC and C_{max}, respectively) in the 6-month repeat-dose GLP toxicology study in the cynomolgus monkey (Study 122293).

4. SELECTION OF STUDY POPULATION

4.1. Inclusion Criteria

Subjects must satisfy all of the following criteria prior to enrollment, unless otherwise stated:

1. Subject has provided informed consent before initiation of any study-specific activities/procedures.
2. Healthy male or female subjects, between 18 and 55 years of age (inclusive) at the time of Screening.
3. Chinese, Japanese, or Caucasian subject:
 - Chinese subjects must be of Chinese ancestry (4 grandparents and biological parents).
 - Japanese subjects must be first- or second-generation Japanese (4 grandparents and biological parents; subject or both of their parents must have been born in Japan).
 - Caucasian subjects are those who self-identify exclusively as such on the electronic case report form (eCRF) and also identify their biological parents as such.
4. In good health, determined by no clinically significant findings from medical history, PE, 12-lead electrocardiogram (ECG), vital signs measurements, and clinical laboratory evaluations (congenital nonhemolytic hyperbilirubinemia [eg, suspicion of Gilbert's syndrome based on total and direct bilirubin] is not acceptable) as assessed by the Investigator (or designee).
5. Body mass index between 17 and 30 kg/m² (inclusive) at the time of Screening.

4.2. Exclusion Criteria

Subjects will be excluded from the study if they satisfy any of the following criteria prior to enrollment unless otherwise stated:

1. History or evidence, at Screening or Check-in, of a clinically significant disorder, condition, or disease not otherwise excluded that, in the opinion of the Investigator (or designee), would pose a risk to subject safety or interfere with the study evaluation, procedures, or completion.
2. Evidence of scars, tattoos, or other skin lesions that may interfere with the injection site or injection site assessments.
3. History or evidence of clinically significant arrhythmia at Screening, including any clinically significant findings on the ECG taken at Check-in.

4. A QT interval corrected for heart rate using Fridericia's method (QTcF) interval > 450 msec in male subjects or > 470 msec in female subjects or history/evidence of long QT syndrome, at Screening or Check-in.
5. PR interval > 210 msec, at Screening or Check-in.
6. Second- or third-degree atrioventricular (AV) block, at Screening or Check-in.
7. Systolic blood pressure (BP) > 140 mmHg or < 90 mmHg, or diastolic BP > 90 mmHg, or HR > 100 bpm, at Screening or Check-in.
8. History of hypersensitivity, intolerance, or allergy to any drug compound, food, or other substance, unless approved by the Investigator (or designee) and in consultation with the Sponsor.
9. Poor peripheral venous access.
10. Estimated glomerular filtration rate less than 60 mL/min/1.73 m² as calculated by the Modification of Diet in Renal Disease equation, at Screening.
11. Underlying condition that predisposes the subject to infections (eg, history of splenectomy).
12. HbA1C ≥ 7%, at Screening or Check-in.
13. Active tuberculosis (TB) requiring treatment or documented latent TB within the previous 3 years. All subjects will be required to have a QuantiFERON-TB Gold test performed at Screening. Also excluded are participants with evidence of a past TB infection without documented adequate therapy. Participants with a positive QuantiFERON-TB Gold test at Screening will not be eligible for the study. A QuantiFERON-TB Gold test performed within 4 weeks of dosing on Day 1 is acceptable as long as there is documentation of a negative result.
14. Subjects who have received live vaccines within 5 weeks prior to Screening, or plan to receive live vaccines within 105 days after administration of an investigational product.
15. Subjects who have received Coronavirus Disease 2019 (COVID-19) vaccine within 28 days prior to dosing, or plan to receive a COVID-19 vaccine within 28 days postdose; from 29 days postdose through EOS, vaccination for COVID-19 may be deemed acceptable for a subject following discussion and agreement between the Sponsor and the Investigator.
16. History of active infections (viral, bacterial, or fungal) within 21 days of receiving the investigational product.
17. Positive hepatitis B or hepatitis C panel (ie, positive hepatitis B surface antigen, hepatitis B core antibody or hepatitis C antibody) at Screening, or a medical history for hepatitis B or C; and/or positive human immunodeficiency virus test, at Screening. Subjects whose results are compatible with prior vaccination may be included. Subjects with a history of hepatitis B vaccination without a history of hepatitis B or C are allowed to participate.
18. Use of any over-the-counter or prescription medications within 30 days or 5 half-lives (whichever is longer) of Check-in. Continued use, if applicable, will be reviewed by the Investigator (or designee) and in consultation with the Sponsor. Written documentation of this review and Sponsor acknowledgment is required for subject participation. Exceptions are listed below.

- Acetaminophen [paracetamol] up to 2 g per day for analgesia will be allowed.
- Hormonal contraception listed in [Appendix 4](#) will be allowed.
- Hormone replacement therapy (eg, estrogen) will be allowed.

19. Use of any herbal medicines, vitamins, or supplements consumed within the 30 days prior to Check-in, unless deemed acceptable by the Investigator (or designee) and in consultation with the Sponsor.

20. Consumption of foods and beverages containing poppy seeds within 7 days prior to Check-in.

21. History of alcoholism or drug/chemical abuse within 1 year prior to Check-in.

22. Alcohol consumption from 48 hours prior to Check-in.

23. Regular alcohol consumption of > 14 units per week for males and > 7 units for females. One unit of alcohol equals ½ pint (285 mL) of beer or lager, 1 glass (125 mL) of wine, or 1/6 gill (25 mL) of spirits.

24. Use of tobacco- or nicotine-containing products within 6 months prior to Check-in.

25. Positive test for illicit drugs, cotinine (tobacco or nicotine use), and/or alcohol use at Screening or Check-in.

26. Consumption of caffeine-containing foods and beverages within 24 hours prior to Check-in.

27. Female subjects with a positive pregnancy test at Screening or Check-in.

28. Female subjects who are lactating/breastfeeding or who plan to breastfeed during the study through 90 days after the EOS visit.

29. Subjects who are unwilling to adhere to contraceptive requirements through 90 days after the EOS visit (see [Appendix 4](#)).

30. Subjects who are unwilling to abstain from sperm donation and ovum donation from Check-in until 90 days after the EOS visit (see [Appendix 4](#)).

31. Male subject with a female partner of childbearing potential and not willing to inform his partner of his participation in this clinical study.

32. Male subject with a pregnant partner or partner planning to become pregnant while the subject is on study through 90 days after the EOS visit.

33. Subject has received a dose of an investigational drug within the past 90 days or 5 half-lives of the drug, whichever is longer, prior to Check-in.

34. Subjects who have previously completed or withdrawn from this study or any other study investigating AMG 592 or have previously received the investigational product.

35. Donation of blood from 90 days prior to Check-in, plasma from 2 weeks prior to Check-in, or platelets from 6 weeks prior to Check-in.

36. Subjects who are unwilling to abide with study restrictions.

37. Subjects who, in the opinion of the Investigator (or designee), should not participate in this study.

38. Subjects with abnormal laboratory results for alanine aminotransferase (ALT) or aspartate aminotransferase (AST) (ie, > upper limit of normal) and total bilirubin (ie, > upper limit of normal) at Screening and Checkin.

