3. INVESTIGATIONAL PLAN

3.1. Overall Study Design and Plan

This will be a Phase 1, single-center, open-label, sequential-group study to investigate the safety, tolerability, and PK of a single SC dose of AMG 592 in 2 groups of healthy Chinese subjects and 1 group of healthy Japanese subjects. In addition, a group of healthy Caucasian subjects will be evaluated at the high dose level for comparison.

Approximately 32 subjects will be enrolled in total, with ^{cc} subjects in each of the following 4 groups:

- Group 1: Chinese subjects (n=■) will receive ^{CCI} ■ AMG 592 given as one ^{CCI} ■ SC injection
- Group 2: Chinese subjects (n=■) will receive ^{CCI} ■ AMG 592 given as one ^{CCI} ■ SC injection
- Group 3: Japanese subjects (n=■) will receive ^{CCI} ■ AMG 592 given as one ^{CCI} ■ SC injection
- Group 4: Caucasian subjects (n=■) will receive ^{CCI} ■ AMG 592 given as one ^{CCI} ■ SC injection.

Potential subjects will be screened to assess their eligibility to enter the study within 28 days prior to dose administration.

Under the initial study design and plan prior to Amendment 2 of the protocol, ^{CCI} ■ ^{cc} subjects in Group 1 and all subjects in Groups 3 and 4 had been enrolled, dosed, and had remained in the CRU up through the earliest discharge day on Day 3. Due to the occurrence of adverse events in subjects administered with AMG 592 reported thus far in the study after day 4 and during the period after discharge from the CRU, enrollment of the remaining ^{cc} subjects in Group 1 was placed on temporary hold. The intention of the hold was to allow a full evaluation of emerging safety data and to prepare protocol amendment 2.

Under Protocol Amendment 2, the overall study design and plan will be conducted as follows, for the remaining ^{cc} subjects in Group 1 (Chinese cohort, ^{CCI} ■) and all subjects in Group 2 (Chinese cohort, ^{CCI} ■):

Eligible subjects will be admitted into the CRU for Check-in on Day -1 and be confined to the CRU until clinic discharge on Day 7. Individual subjects may be required to remain in the CRU for safety observations beyond Day 7 (to a maximum of Day 11) at the discretion of the Investigator, based on the emergence and progression of adverse events and other signs and symptoms requiring monitoring. Each subject will participate in 1 treatment group only.

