For subjects to be enrolled under Amendment 2, after discharge from the CRU on Day 7, subjects will return for outpatient visits on Days 8, 11, 15, 22, 29, and the end of study (EOS) visit on Day 43. (For subjects enrolled prior to Amendment 2 and discharged on Day 3, outpatient visits also included Days 4, 5, and 6.) It is anticipated that many subjects will be traveling a great distance to the CRU in order to participate in the study; therefore, to reduce unnecessary travel and ease the burden on subjects needing to find local accommodations for the frequent outpatient visits in the first 2 weeks of the study, subjects may reside in the CRU after clinic discharge on Day 7 through a maximum of Day 11. In addition to this elective option to remain in the CRU, individual subjects may be required to remain in the CRU beyond Day 7 (to a maximum of Day 11) at the discretion of the Investigator, based on the emergence and progression of adverse events or signs/symptoms of other adverse drug reactions. To summarize, a subject may leave the CRU after discharge procedures on Day 7, unless required to stay by the Investigator or, if not required to stay, may elect to stay voluntarily; in either case, residence in the CRU may be through a maximum of Day 11. Subjects who remain in the CRU beyond Day 7 will have the applicable scheduled outpatient procedures performed while resident. A subject's participation in the study will conclude at the completion of the EOS visit; however, subjects who test positive at EOS for neutralizing antibodies to IL-2 or binding antibodies with potentially antibody-mediated clinical sequelae will be asked to return for additional follow-up testing every 3 months until antibodies are no longer detected or up to 12 months (\pm 4 weeks) post administration of AMG 592 (whichever is shorter).

The total duration of study participation for each subject (from screening through the EOS visit) is anticipated to be approximately 10 weeks.

The start of the study is defined as the date the first subject signs an informed consent form (ICF). The point of enrollment occurs at the time of subject number allocation. The end of the study is defined as the date of the last subject's last assessment (scheduled or unscheduled).

An overview of the study design is shown in [Figure 1](#). A Schedule of Assessments is presented in [Appendix 8](#).

Figure 1: Study Design

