6. CONCOMITANT THERAPIES AND OTHER RESTRICTIONS

6.1. Concomitant Therapies

Subjects will refrain from use of any prescription or nonprescription medications/products during the study until the EOS visit, unless the Investigator (or designee) and/or Sponsor have given their prior consent.

Acetaminophen (paracetamol) (2 g/day), hormone replacement therapy or oral, implantable, transdermal, injectable, or intrauterine contraceptives are acceptable concomitant medications. The administration of any other concomitant medications during the study is prohibited without prior approval of the Investigator (or designee), unless its use is deemed necessary for treatment of an adverse event. Any medication taken by a subject during the course of the study and the reason for its use will be documented in the source data.

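### Exclusion criterion 14 does not cover a live vaccine given between Screening and dosing

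*Protocol*

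**What the plan says.** Criterion 14 in Protocol Section 4.2 has two limbs. It excludes "Subjects who have received live vaccines within 5 weeks prior to Screening, or plan to receive live vaccines within 105 days after administration" of the investigational product. Section 3.1 sets the Screening window: "Potential subjects will be screened to assess their eligibility to enter the study within 28 days prior to dose administration". Appendix 8 places Screening on Day -28 to Day -2, Check-in on Day -1 and dosing on Day 1.

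Three other provisions bear on the same interval:

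- **Criterion 15** is the only other criterion that sets a rule for receiving a vaccine. It excludes "Subjects who have received Coronavirus Disease 2019 (COVID-19) vaccine within 28 days prior to dosing" and those planning one within 28 days after. It then sets a permission route, decided jointly by sponsor and investigator: "from 29 days postdose through EOS, vaccination for COVID-19 may be deemed acceptable for a subject following discussion and agreement".
- **Criterion 18** excludes "Use of any over-the-counter or prescription medications within 30 days or 5 half-lives (whichever is longer) of Check-in". It provides for review of continued use: "Written documentation of this review and Sponsor acknowledgment is required for subject participation".
- **Section 6.1** states that "Subjects will refrain from use of any prescription or nonprescription medications/products during the study until the EOS visit", unless the investigator and/or sponsor has consented beforehand. Section 3.1 counts participation from Screening: "The total duration of study participation for each subject (from screening through the EOS visit) is anticipated to be approximately 10 weeks".

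Neither criterion 18 nor Section 6.1 mentions vaccines.

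**The concern.** The backward limb is tied to Screening and the forward limb to dosing, and the two events can be four weeks apart. Whatever falls between them is outside the one criterion written for live vaccines. A subject who says at Screening that a live vaccine is booked before dosing also meets neither limb.

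With early Screening the order is inverted: an older vaccination excludes and a more recent one does not. If the aim is to keep live vaccination away from exposure to an immunomodulatory product, the uncovered period is the one closest to exposure. Protection then depends on the site reading a vaccine as a medication or product under the general rules, which can in some circumstances be relaxed by review or consent. Criterion 14 has no such route.

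The end-point looks like a drafting slip. The other dated exposure look-backs in Section 4.2 end at Check-in (criteria 18 to 22, 24, 26, 33 and 35) or at dosing (criteria 15 and 16).

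**Working it through.** The plan gives no figure to reproduce; the check is a day count on its own anchors.

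**Inputs.** Look-back of 5 weeks = 35 days before Screening, and forward limb of 105 days after dosing (criterion 14). Screening on Day -28 to Day -2, Check-in on Day -1, dosing on Day 1 (Appendix 8). There is no Day 0, so Screening on Day -k is k days before dosing, with k from 2 to 28.

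**Coverage of the first limb.** It covers k to k + 35 days before dosing. The stretch in neither limb is the k days that end at dosing.

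| Screening day | k | Covered (days before dosing) | Length of gap |
|---|---|---|---|
| Day -28 | 28 | 28 to 63 | 28 days |
| Day -10 | 10 | 10 to 45 | 10 days |
| Day -2 | 2 | 2 to 37 | 2 days |

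**Two example vaccines.**

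- Given 10 days before dosing: covered only if k ≤ 10. That is Day -10 to Day -2, or 9 of the 27 possible Screening days. It is missed for Day -28 to Day -11, the other 18.
- Given 60 days before dosing: covered only if 60 - k ≤ 35, so k ≥ 25. That is Day -28 to Day -25.

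For Screening on Day -28 to Day -25, therefore, the 60-day vaccine excludes and the 10-day vaccine does not. With Screening on Day -2 the 10-day vaccine excludes and the inversion largely disappears. The 18 of 27 counts calendar days for one example; it is not a probability.

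**Reach of criterion 18.** Thirty days before Check-in is 30 + 1 = 31 days before dosing. Since 31 > 28, it spans the whole gap up to Check-in for every permitted Screening day, provided that a vaccine is a medication.

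**Two possible repairs.**

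- Extend the first limb through dosing: coverage becomes 0 to k + 35 days, which is 0 to 63 (k = 28) or 0 to 37 (k = 2). Nothing now excluded is lost.
- Count the 5 weeks back from dosing instead: coverage becomes 0 to 35 days. The gap closes, but vaccines given 36 to 63 days before dosing are no longer excluded when k = 28, and those at 36 to 37 days when k = 2.

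**Subjects concerned.** Under Amendment 2 only the rest of Group 1 and all of Group 2 remain to be enrolled. At 32/4 = 8 per group, that is fewer than 2 × 8 = 16.

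**The case against.** The strongest reply is that criterion 14 should not be read alone. If a vaccine is a medication, criteria 14 and 18 together cover 1 to k + 35 days before dosing without a break for every permitted Screening day, and the subject is confined to the unit from Check-in. The inversion then vanishes. Criterion 18 may even be the stricter rule here: its review route is for continued use, which a single vaccination is not obviously, and vaccines are not among its listed exceptions. Section 4.5 (withdrawal from dosing) and criteria 36 and 37 give the investigator further discretion before dosing.

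This stands as far as it goes, and is why the point is small. It rests on a reading that the text does not settle. Criterion 15 can be argued either way. Its separate permission after Day 28 postdose makes sense if Section 6.1 already bars vaccines. But its 28-day predose limb would sit almost wholly inside criterion 18 if vaccines were medications, which suggests that vaccines were meant to have their own rules. The finding does not depend on which inference is right.

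It is also fair to say that a 5-week washout before dosing may be what the authors intended, and that counting from dosing would close the gap too. Without a stated rationale, neither intent can be shown. Extending the limb through dosing is preferred only because it removes no existing exclusion.

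**Conclusion.** The concern holds, as a minor point. As worded, criterion 14 leaves the 2 to 28 days before dosing in neither limb, and this part follows directly from the text. Whether a subject could be dosed soon after a live vaccine depends on the site not treating the vaccine as a medication or product under criterion 18 or Section 6.1.

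The protocol describes no specific harm from a live vaccine before AMG 592, so the stake is a presumed safety margin. The documents give no distribution of Screening days and no frequency of live vaccination, so the number affected cannot be estimated beyond the ceiling of fewer than 16 still to be enrolled; it is likely to be few or none.

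**What to change.** Reword the first limb of criterion 14 to exclude live vaccines received *from 5 weeks before Screening through dosing on Day 1*, and leave the 105-day limb as it is. Check it at Check-in, where the interim medical history and the concomitant therapy review are already scheduled (Appendix 8). Do not simply move the 5-week count to dosing unless the sponsor confirms that the shorter window is intended.

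The cost is one reworded limb, no new visit or procedure, and at most a rare extra exclusion or a delayed dose.

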4.5. Subject Withdrawal and Replacement

A subject is free to withdraw from the study at any time. In addition, a subject will be withdrawn from dosing if any of the following criteria are met:

- change in compliance with any inclusion/exclusion criterion that is clinically relevant and affects subject safety as determined by the Investigator (or designee)
- noncompliance with the study restrictions that might affect subject safety or study assessments/objectives, as considered applicable by the Investigator (or designee)
- any clinically relevant sign or symptom that, in the opinion of the Investigator (or designee), warrants subject withdrawal.

If a subject is withdrawn, the Sponsor will be notified and the date and reason(s) for the withdrawal will be documented in the subject's eCRF, and efforts will be made to perform all EOS assessments, if possible ([Appendix 8](#)). Other procedures may be performed at the Investigator's (or designee's) and/or Sponsor's discretion. If the subject is residing at the CRU, these procedures should be performed before the subject is discharged from the clinic. The Investigator (or designee) may also request that the subject return for additional follow-up visit(s). All withdrawn subjects will be

followed until resolution of all their adverse events or until the unresolved adverse events are judged by the Investigator (or designee) to have stabilized.

Subjects who are withdrawn for reasons not related to study drug may be replaced following discussion between the Investigator and the Sponsor. Subjects withdrawn as a result of adverse events thought to be related to the study drug will generally not be replaced.

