7.5.2. Clinical Laboratory Evaluations

Blood and urine samples will be collected for clinical laboratory evaluations (including clinical chemistry, hematology, urinalysis, and serology) at the times indicated in the Schedule of Assessments in [Appendix 8](#). Clinical laboratory evaluations are listed in [Appendix 2](#).

The Investigator is responsible for reviewing laboratory test results and recording any clinically relevant changes occurring during the study in CRF/eCRF. The Investigator must determine whether an abnormal value in an individual study subject represents a clinically significant change from the subject's baseline values. In general, abnormal laboratory findings without clinical significance (based on the Investigator's judgment) are not to be recorded as adverse events. However, laboratory value changes that require treatment or adjustment in current therapy are considered adverse events. Where applicable, clinical sequelae (not the laboratory abnormality) are to be recorded as the adverse event.

Subjects will be asked to provide urine samples for drugs of abuse screen and cotinine test, and will undergo an alcohol breath test at the times indicated in the Schedule of Assessments in [Appendix 8](#). For all female subjects, a pregnancy test and follicle-stimulating hormone screen for postmenopausal status will be performed at the times indicated in the Schedule of Assessments in [Appendix 8](#).

An Investigator (or designee) will perform a clinical assessment of all clinical laboratory data.

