4.2. Exclusion Criteria

Subjects will be excluded from the study if they satisfy any of the following criteria prior to enrollment unless otherwise stated:

1. History or evidence, at Screening or Check-in, of a clinically significant disorder, condition, or disease not otherwise excluded that, in the opinion of the Investigator (or designee), would pose a risk to subject safety or interfere with the study evaluation, procedures, or completion.
2. Evidence of scars, tattoos, or other skin lesions that may interfere with the injection site or injection site assessments.
3. History or evidence of clinically significant arrhythmia at Screening, including any clinically significant findings on the ECG taken at Check-in.
4. A QT interval corrected for heart rate using Fridericia's method (QTcF) interval > 450 msec in male subjects or > 470 msec in female subjects or history/evidence of long QT syndrome, at Screening or Check-in.
5. PR interval > 210 msec, at Screening or Check-in.
6. Second- or third-degree atrioventricular (AV) block, at Screening or Check-in.
7. Systolic blood pressure (BP) > 140 mmHg or < 90 mmHg, or diastolic BP > 90 mmHg, or HR > 100 bpm, at Screening or Check-in.
8. History of hypersensitivity, intolerance, or allergy to any drug compound, food, or other substance, unless approved by the Investigator (or designee) and in consultation with the Sponsor.
9. Poor peripheral venous access.
10. Estimated glomerular filtration rate less than 60 mL/min/1.73 m² as calculated by the Modification of Diet in Renal Disease equation, at Screening or Check-in.
11. Underlying condition that predisposes the subject to infections (eg, history of splenectomy).
12. HbA1C ≥ 7%, at Screening or Check-in.
13. Active tuberculosis (TB) requiring treatment or documented latent TB within the previous 3 years. All subjects will be required to have a QuantiFERON-TB Gold test performed at Screening. Also excluded are participants with evidence of a past TB infection without documented adequate therapy. Participants with a positive QuantiFERON-TB Gold test at Screening will not be eligible for the study. A QuantiFERON-TB Gold test performed within 4 weeks of dosing on Day 1 is acceptable as long as there is documentation of a negative result.
14. Subjects who have received live vaccines within 5 weeks prior to Screening, or plan to receive live vaccines within 105 days after administration of an investigational product.

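### Exclusion criterion 38, read literally, is not triggered by a combined liver-test elevation first seen at Check-in on Day -1

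*Protocol*

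**What the plan says.** Section 4.2 of the current protocol (Amendment 2) excludes a subject who satisfies any listed criterion. Criterion 38 has two parts: ALT or AST above the upper limit of normal, "and total bilirubin (ie, > upper limit of normal) at Screening and Checkin".

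Other criteria that name the same two visits join them differently. The closest laboratory comparator is criterion 12: "HbA1C ≥ 7%, at Screening or Check-in". Criteria 1, 4, 5, 6, 7, 25 and 27 also use *or*. Criterion 10 (eGFR) now names one visit only: "as calculated by the Modification of Diet in Renal Disease equation, at Screening".

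The schedule in Appendix 8 draws chemistry at Screening and again at Check-in, and Section 3.1 places Check-in on Day -1. Section 4.3 allows one repeat of an out-of-range screening laboratory result. It permits enrollment if the repeat is in range, unless the Investigator or Sponsor disallows this for a critical test.

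**The concern.** A subject is excluded only when a criterion is met. If criterion 38 needs the abnormality at both visits, a subject with normal liver tests at Screening and a combined elevation on Day -1 does not meet it. The Check-in result could then complete an exclusion but never cause one.

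This matters because the Check-in sample is the last scheduled liver chemistry before a single dose that cannot be withdrawn. Criterion 38 is also the only place where eligibility carries a numeric ALT, AST or bilirubin limit. It governs the subjects enrolled under Amendment 2, which are the remaining Group 1 subjects and the whole of Group 2, the dose-escalation cohort. If the numeric rule is silent, two people applying the protocol to the same Day -1 result could reach different decisions.

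**Working it through.** The documents state no figure on this point, so the check is a reading of the text.

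**1. Possible cases.** Call a combined elevation ALT or AST above the upper limit together with total bilirubin above the upper limit. Compare the outcome under criterion 38 alone.

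| Combined elevation at Screening | Combined elevation at Check-in | Literal *and* | Phrase only names the visits tested | *or* |
|---|---|---|---|---|
| yes | yes | excluded | excluded | excluded |
| no | yes | **not excluded** | excluded | excluded |
| yes | no | not excluded | excluded, subject to Section 4.3 | excluded, subject to Section 4.3 |
| no | no | not excluded | not excluded | not excluded |

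The second row is the point. The third row is weaker. Under Section 4.3 a Screening abnormality that clears on one repeat can lead to enrollment whichever conjunction is used, so enrolling some of these subjects is stated policy.

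**2. Which reading does the protocol favor?**
- For the literal reading: eight other criteria (1, 4, 5, 6, 7, 12, 25 and 27) pair the visits with *or*, so a reader will expect *and* to mean something different.
- For the visit-list reading: footnote c of Appendix 2 joins the same two visits with *and* simply to say when certain tests are run.

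Neither settles the matter, so the text is ambiguous.

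**3. Is there a reason to ignore a Check-in value?** Criterion 10 is a useful contrast. In the Amendment 1 text it read "as calculated by the Modification of Diet in Renal Disease equation, at Screening or Check-in". Amendment 2 cut it to Screening and also removed the Check-in eGFR from the schedule. That is a consistent, deliberate change. Chemistry was not removed from Check-in, so the data for an *or* rule are already collected.

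**4. What is left if criterion 38 is silent?**
- Inclusion 4 requires good health on laboratory evaluations, including no suspected Gilbert's syndrome, as the Investigator assesses.
- Exclusion 1 covers "History or evidence, at Screening or Check-in, of a clinically significant disorder, condition, or disease not otherwise excluded", in the Investigator's opinion.
- Exclusion 37 is a general Investigator opinion clause.
- Section 4.5 withdraws a subject from dosing for "change in compliance with any inclusion/exclusion criterion that is clinically relevant and affects subject safety as determined by the Investigator (or designee". If criterion 38 is not met, this trigger cannot act through criterion 38, though it can act through the others.
- Section 7.5.2 states: "An Investigator (or designee) will perform a clinical assessment of all clinical laboratory data".

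All five apply to a Day -1 result, and none contains a numeric limit.

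**5. Whom does it affect?** The Amendment 1 list ends at criterion 37, so criterion 38 applies only from Amendment 2. About 32 subjects in 4 groups gives 32 / 4 = 8 per group. Groups 1 and 2 together are 8 + 8 = 16, and part of Group 1 was dosed earlier, so fewer than about 16 dosed subjects can fall under it.

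**The case against.** The strongest reply is that the phrase lists the visits at which the liver tests count, as Appendix 2 footnote c does. The eight criteria using *or* were already in the Amendment 1 text, whereas criterion 38 was appended later, after the general opinion clause, so the older wording is weak evidence of what its drafter meant. This stands as far as it goes: on that reading the gap is nil. But *or* states that same rule without ambiguity, so the edit loses nothing.

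A second reply is that *and* was meant to require confirmation. Section 4.3 already provides a repeat for Screening results, and confirmation would not explain passing an abnormality that is new on Day -1.

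A third is that judgment covers the case. A competent Investigator would be likely to stop such a subject, and with a single center one clarification reaches everyone. This lowers the practical risk considerably. It does not restore a numeric limit at the last pre-dose chemistry. Appendix 7 has a rule for subjects with raised values before exposure, but it acts only after dosing.

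A reader might infer more than the documents support:
- **That such a subject must be dosed.** The five judgment-based protections remain in force.
- **That *or* would exclude every Screening-only elevation.** Section 4.3 allows some of those subjects in after a normal repeat.
- **That pairing transaminases with bilirubin is itself a mistake.** The pairing resembles the liver-injury signal in Appendix 7, and nothing shows it was unintended.
- **That the adverse events behind the enrollment hold were hepatic.** The protocol does not say so.

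**Conclusion.** The point holds in a narrow form. On a literal reading, a combined elevation first seen on Day -1 escapes the only numeric liver-test exclusion and is decided by Investigator judgment. On the other available reading there is no gap. Confidence is medium because the intended meaning cannot be established from the documents.

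The size cannot be estimated. No abnormality rates are given and the number of remaining Group 1 subjects is redacted. The bound of fewer than about 16 dosed subjects assumes the planned equal group sizes. The primary PK endpoints and the SAP analyses are not defined by this criterion, so the issue is eligibility and subject safety rather than inference. It is worth correcting because the rule is live for the escalation cohort and the correction is small.

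**What to change.** In criterion 38, replace the conjunction between the two visits so that it reads Screening *or* Check-in, matching criterion 12. State that the Section 4.3 single-repeat rule continues to apply to Screening results. While the sentence is open, the sponsor's medical team can confirm that the transaminase-plus-bilirubin combination is the one intended; no change to it is requested.

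The cost is one word in an amendment or clarification memo. No new samples are needed, because chemistry is already drawn at Check-in. The downside is possibly a few more exclusions at Check-in among the remaining Group 1 and Group 2 candidates, after they have been admitted.
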